We will provide the first objective data that looks at the additional energy expenditure necessary for inactive adults with a lower-limb amputation who are using a prosthesis to walk short-distances as compared to able-bodied adults; this data may be used for the development of future prosthetic components that reduce energy expenditure. We will explore factors that may be linked to energy expenditure and physical activity among adults with and without a lower-limb amputation.

Specific Aim 1: Evaluate reliability and validity of physical activity self-report measures (i.e. International Physical Activity Questionnaire, Incidental and Planned Exercise Questionnaire-past week^{23,24}) as compared to physical activity characteristics obtained via step activity monitors (i.e. time spent walking/day, walking bout duration, walking bouts/day) among inactive adults with a single-limb amputation (n=20).

Hypothesis: *H1a: Both self-report measures will have excellent test-retest reliability (ICCs $\geq .75$). H1b: At least 1 self-report measure will demonstrate validity with ≥ 2 physical activity characteristics.*

Specific Aim 2: Determine what gait speed (mph) and cadence (steps/minute) constitute 3 METs, i.e. moderate-intensity activity, among inactive adults with a single, below-the-knee amputation during over-ground and treadmill walking (n=20).

Hypothesis: *H2a: 3 METs will occur at slower speeds during treadmill walking as compared to over-ground walking. H2b: 3 METs will occur at slower cadences during treadmill walking as compared to over-ground walking.*

Specific Aim 3: Evaluate differences in energy expenditure based on oxygen consumption between inactive adults with a single, below-the-knee amputation (n=20) and matched controls (n=20) during short bouts of over-ground and treadmill walking at self-selected gait speeds, 75% and 125% of self-selected gait speeds.

Hypothesis: *H3: Energy expenditure will be significantly greater at all walking speeds for adults with a limb amputation as compared to controls (a) over-ground and (b) during treadmill walking ($p \leq 0.05$).*

Specific Aim 4: Explore modifiable factors that may impact energy expenditure (assessed via oxygen consumption) including comorbidities, fatigue, sleep disturbance, balance, functional lower extremity strength, functional mobility, and agility among adults with (n=20) and without a unilateral below-the-knee amputation (n=20).

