Participants will be fit with a mobile gait analysis system (APDM Mobility Lab) that will assess gait symmetry during the over-ground and treadmill walking tests that follow. Participants will be fit with APDM Mobility Lab sensors at the following locations: sternum, posterior surface of both wrists, lumbar spine, anterior surface of both thighs, anterior surface of both lower legs (and/or the sound lower leg and the prosthetic leg), and the dorsal surface of both feet (and/or the sound foot and prosthetic foot). This will take approximately 5 minutes.

The APDM software will be used to collect spatio-temporal measurements, such as stride length and velocity, as well as three-dimensional kinematic measurements, including joint position and acceleration throughout the gait cycle and maximal toe clearance during the swing phase of gait. Information regarding trunk sway and arm swing will also be collected.

Participants will also be fit with a Polar heartrate monitor, worn around the chest on the skin, to allow vital sign monitoring during the over-ground and treadmill walking conditions. The examiner will wear the wristwatch monitoring unit during the walking bouts for ease of monitoring.

Gait Speed Pre- and Post-Walking Conditions Assessment

We will use a computerized walkway system (GaitRite) to obtain self-selected (3 trials) and fast-walking speeds (3 trials) as well as other spatiotemporal parameters of gait immediately before and after each walking condition. APDM sensor data collection will also occur during self-selected and fast walking trials over the GaitRite system. By comparing pre- and post-walking gait speeds, we may be able to determine if the participant experienced fatigue during the walking bout. This will take <3 minutes per collection; there will be 4 collections total.

Metabolic Cost Testing Procedures. Participants will have their metabolic energy expenditure (i.e. oxygen consumption) measured as they walk at various speeds within the Department of Physical Therapy. Individuals with a unilateral transtibial amputation will complete the following two tests in a randomized order (controls will complete the tests in the same order as their matched participant with a unilateral transtibial amputation):

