1. 3-Stage Walking Metabolic Gas Analysis on Treadmill Test: Oxygen consumption measurements will be performed with the participant walking on a treadmill, set to three different speeds. After being fitted with the metabolic gas analysis equipment, participants will sit in a chair for five minutes to collect baseline oxygen consumption. Then, participants will walk on the treadmill at a constant speed that will be derived from the participant's self-selected gait speed as measured by the GAITRite™ walkway. In stage 1, participants will walk at 75% of their self-selected gait speed for 2.5 minutes. In stage 2, participants will walk at 100% of their self-selected gait speed for 2.5 minutes. In stage 3, participants will walk at

125% of their self-selected gait speed for 2.5 minutes. These speeds were selected based on pilot data in 44 patients with a unilateral transtibial amputation who walked on average at a mean self-selected speed of .88 m/sec (95% CI: .80, .95) if they were K3 functional level and 1.16 (1.06, 1.25) if they were K4 functional level and a mean fast gait speed of 1.15 (1.05, 1.25) and 1.53 (1.38, 1.68) if they were K3 and K4 functional level, respectively. Available safety features will be used with treadmill testing (e.g. lanyards, emergency stops).

In-between stages, participants will sit until their heart rate returns below 100 beats per minute. This methodology has been derived from prior studies with similar purposes.^{12, 25, 26} During each stage, the investigator will measure the number of steps taken using a hand tally counter; step cadence (i.e. steps/minute) will be computed from this value.

The Oxycon Mobile™ (CareFusion™, San Diego, CA) Portable VO₂ Measurement system will be used to collect expired air via a facemask to measure VO₂ uptake; this device is a lightweight, non-cumbersome machine used for portable metabolic measurement. The O₂ and CO₂ analyzers will be calibrated at the beginning of each test using standard calibration gases (16% O₂, 4% CO₂, balance nitrogen; CareFusion™, San Diego, CA). The auto calibration function will be used to calibrate volume (CareFusion™, San Diego, CA).

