2. **3-Stage Walking Metabolic Gas Analysis Over-Ground Test:** Oxygen consumption measurements will be performed with the participant walking over ground in an uncarpeted corridor on a course consisting of two cones, 20-meters apart. Similar to the treadmill test, participants will be asked to walk at three different speed. After being fitted with the metabolic gas analysis equipment, participants will sit in a chair for five minutes to collect baseline oxygen consumption. Then, participants will complete the walking test in three stages. In stage 1, participants will be instructed to walk at their “slow” speed for 2.5 minutes. In stage 2, participants will be instructed to walk at their “usual, comfortable” speed for 2.5 minutes. In stage 3, participants will be asked to walk at their “brisk” speed for 2.5 minutes. In between stages, participants will sit until their heart rate returns below 100 beats per minute. This methodology has been derived from prior studies with similar purposes.^{12, 25, 26} Again, the Oxycon Mobile™ will be used to complete these measurements. During each stage, the investigator will measure the number of steps taken using a hand tally counter; step cadence will be computed from this value (i.e. steps/minute). Also, the distance the participant covers within each stage will be recorded.

Step Activity Monitoring.

At the conclusion of the on-site evaluation, all participants will be equipped with the StepWatch Activity Monitor. The activity monitor will be fastened near the ankle of the prosthesis using the straps included with the monitor (or in the case of controls, around the ankle joint of the right side).

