Specific Aim 1: To determine reliability, intra-class correlation coefficients (ICCs) with 95% confidence intervals (CIs) will be calculated to evaluate test-retest reliability of physical activity

questionnaires. To evaluate validity between the self-report questionnaire data and activity-monitor obtained data that is continuous (e.g. steps/day, total activity in minutes/day), we will use ICCs with 95% CIs. We will quantify the relationship between the self-report data and activity-monitor data using Spearman's correlation coefficients. Interpretation will be as follows: $p \leq .25$ =weak correlation, $p=.26\text{--}.49$ =low correlation, $p=.50\text{--}.69$ =moderate correlation, $p \geq .70$ =high correlation.

Specific Aim 2: We will use receiver operating characteristic (ROC) curves to determine the minimal speed and cadence that corresponds to an oxygen consumption value of 10.5 mL/kg/min (i.e. 3.0 METs), as this has been identified by the World Health Organization as 'moderate intensity' activity.¹⁰

Specific Aims 3 and 6-10: We will use a MANOVA/MANCOVA to evaluate between-group differences with follow-up ANOVAs/ANCOVAs as appropriate ($p \leq 0.05$).

Specific Aims 4/5: Regression models will be used to explore relationships between energy expenditure (or average daily step counts) and each of the modifiable factors of interest, while controlling for relevant non-modifiable covariates, e.g. age, residual limb length.

Reported

Dissemination of results will occur through conference presentations and manuscript publications in peer-reviewed journals.

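### The order of the two walking tests is randomised and copied to controls but enters no analysis, which costs precision if the second test differs from the first

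*Combined protocol and SAP*

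**What the plan says.** Section 6 (Metabolic Cost Testing Procedures) has two three-stage tests, treadmill and over-ground. Participants with an amputation "will complete the following two tests in a randomized order", and "controls will complete the tests in the same order as their matched participant with a unilateral transtibial amputation". The method of randomisation (simple, blocked or balanced) is not stated.

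Each test opens with a rest: "participants will sit in a chair for five minutes to collect baseline oxygen consumption". Between stages, "participants will sit until their heart rate returns below 100 beats per minute". No other recovery period between the two tests is described.

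Gait speed is measured on the walkway before and after each condition, with this purpose: "By comparing pre- and post-walking gait speeds, we may be able to determine if the participant experienced fatigue during the walking bout". Section 10 does not use these measurements.

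H2a in section 5 states that "3 METs will occur at slower speeds during treadmill walking as compared to over-ground walking"; H2b says the same for cadence. Both compare the two conditions within the amputation group. For Aim 2, section 10 gives only ROC curves against 10.5 mL/kg/min. For Aims 3 and 6-10: "We will use a MANOVA/MANCOVA to evaluate between-group differences with follow-up ANOVAs/ANCOVAs as appropriate", with no covariates named. For Aims 4 and 5 the example covariates are age and residual limb length. Order, sequence and period appear nowhere in section 10.

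**The concern.** A factor that the design randomises, and deliberately carries over to controls, would normally be in the model. The participants are chosen to be inactive, both tests fall within one visit of about two hours, and the protocol itself allows for fatigue. If the second test differs systematically from the first, that difference widens the spread of the treadmill minus over-ground differences. With about 20 people in the amputation group there is little precision to spare for H2a and H2b. If simple randomisation leaves the two orders uneven, part of the period effect also enters the estimate in that particular sample.

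**Working it through.** The documents contain no power calculation, so there is no figure of the plan's to reproduce. The check uses a paired comparison as the simplest form of the missing H2 test.

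**Inputs.** n = 20 (section 5, Aim 2). Two-sided alpha of 0.05: the level is in sections 5 and 10, the sidedness is assumed. The condition effect (0.65) and the period effect (0 to 1.0) are assumptions, in units of the SD of the within-person difference.

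**Model.** For participant i, treadmill minus over-ground is d = tau + s·pi + e, with s = +1 if the treadmill test comes second, s = −1 if it comes first, and SD(e) = 1. The analysis without order is a one-sample t-test on d (19 degrees of freedom). The analysis with order averages the two order-specific means and pools the variance within order (18 degrees of freedom).

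**Expectation.** Under randomised order E(s) = 0, so E(mean d) = tau. In simulation the mean bias was at most 0.003 SD, with or without the order term.

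**Error.** Ignoring order raises the SD of d from 1 to about √(1 + pi²):
- pi = 0.25: √1.0625 = 1.03
- pi = 0.5: √1.25 = 1.12
- pi = 1.0: √2 = 1.41

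**Power with a 10/10 split and tau = 0.65** (noncentrality 0.65 × √20 = 2.91):

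| Period effect (SD) | Without order | With order |
|---|---|---|
| 0 | 79% | 79% |
| 0.25 | 77% | about 79% |
| 0.5 | 71% | about 79% |
| 1.0 | 48% | about 79% |

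At a period effect of zero the exact values are 78.7% without the term and 78.5% with it.

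Under simple randomisation (simulated at tau = 0.66), power without order at the same three non-zero period effects is 78%, 71% and 50%; with order it is 77-78%. At zero it is 80% without and 78% with, so the term costs about 2 points if the split is left to chance.

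**Type I error without order.** With a 10/10 split the test becomes conservative: 4.5% at 0.25 SD, about 3% at 0.5 SD and under 1% at 1.0 SD. Under simple randomisation it stays near 5%.

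**Chance shift.** In a realised sample with n2 taking the treadmill second and n1 first, the shift is pi × (n2 − n1)/n. At 12/8 this is pi × 4/20 = 0.2 pi, or 0.10 SD for pi = 0.5. The standard error with no order effect is 1/√20 = 0.22 SD. Under simple randomisation of 20, a split of 12/8 or worse has probability 0.50, and 14/6 or worse 0.115. The direction is random.

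**Aim 3.** Copying the order gives matched groups the same split, so a common order effect cancels from the group difference. It remains in the error. With 20 per group, an assumed group difference of 0.9 between-person SD and an assumed second-test effect of 0.5 between-person SD, power is about 77% without order and 79% with it.

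**The case against.** A reader might infer that leaving order out biases the treadmill versus over-ground comparison. The documents do not support that. Order is randomised, so a common second-test effect cancels in expectation. An uneven split produces sampling error of random direction, and the test without order does not reject too often. A reader might likewise infer bias in Aim 3, but the copied order already protects that contrast. The exception is minor: section 6 plans 22 participants with an amputation and 20 controls, so two may have no matched control.

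The power figures rest on chosen inputs. The fall to 48% needs a period effect about 1.5 times the condition effect under test (1.0/0.65); at 0.25 SD the loss is about 2 points. The protocol's remark on fatigue concerns change within a walking bout, not from one test to the next, and short stages with seated recovery make a large effect less likely.

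Finally, section 10 contains no treadmill versus over-ground model to which a term could be added. That is correct, and the missing comparison is the larger gap.

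What survives is narrower: a factor fixed by randomisation is unused, its effect is unknown, and including it costs little.

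**Conclusion.** The omission is real, and its consequence is loss of precision, not bias in expectation. For the within-person H2 contrast the loss ranges from nothing (no period effect) through about 2 points of power at 0.25 SD and 8 points at 0.5 SD to about 30 points at 1.0 SD. These figures rest on 20 participants, a 10/10 order, a 0.65 SD condition effect and a paired comparison that the plan does not yet contain. For Aim 3 the gain is about 2 points under the assumptions shown. This is a low-priority improvement, best made when the H2a/H2b comparison is written. True bias would need carry-over that differs by which test came first. The documents neither show this nor rule it out.

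**What to change.** 1. Section 10, Aim 2: specify the treadmill versus over-ground comparison for H2a and H2b as a within-person model. One option is a mixed model of oxygen consumption on speed (and, separately, cadence) with condition, period (first or second test) and a participant effect. Test the condition contrast from that model; the ROC curves can stay for the thresholds.
2. Section 10, Aim 3: name order as a factor in the MANCOVA, each control carrying the matched participant's order.
3. Section 6: state how order is randomised. A balanced or blocked list would limit the chance shift and the cost of the term.
4. Say how the gait speeds before and after each condition will be used, and which walkway measurement sets the treadmill speeds; one taken after the first test could itself depend on order. Reconcile 22 with 20 participants in the amputation group.

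The cost is wording and one degree of freedom per model. Order must already be known, since it is passed to the matched control. The period term does not remove carry-over that differs by sequence, and that limitation should be stated.

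### The over-ground test includes repeated turns and the treadmill test has none, so the H2 comparison mixes turning with walking surface and may understate the over-ground 3-MET speed

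*Combined protocol and SAP*

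**What the plan says.** Section 6 describes the over-ground metabolic test as "walking over ground in an uncarpeted corridor on a course consisting of two cones, 20-meters apart". There are three self-paced stages (slow, usual, brisk). In the middle one, for example, "participants will be instructed to walk at their “usual, comfortable” speed for 2.5 minutes". Steps are counted by hand tally over the whole stage to give cadence, and "the distance the participant covers within each stage will be recorded". The text does not describe how participants round the cones, count the turns, or say how over-ground speed is derived.

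The treadmill test in the same section is different in kind: "participants will walk on the treadmill at a constant speed that will be derived from the participant's self-selected gait speed", at 75%, 100% and 125% of that speed, again for 2.5 minutes each.

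Section 5 (Specific Aim 2) states H2a as "3 METs will occur at slower speeds during treadmill walking as compared to over-ground walking". H2b makes the same prediction for cadence. Section 10 analyses Aim 2 with ROC curves at 10.5 mL/kg/min and mentions no handling of turns.

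For Aim 7, Section 6 (Pre-Walking Set-Up) fits a sensor system "that will assess gait symmetry during the over-ground and treadmill walking tests that follow". The sensors also record stride length and velocity, and they run during the GaitRite walkway trials before and after each walking condition.

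**The concern.** A 20-m course cannot be walked for 2.5 minutes without repeatedly reversing direction. Turning is therefore present in one condition of the H2 comparison and absent from the other. Section 5 motivates that comparison by gait symmetry on the two surfaces, and turning is a separate mechanism. The protocol itself tests turning and curved-path walking as abilities in their own right (L-Test, Figure of 8). Randomizing the order of the two tests balances order effects but leaves this difference in place.

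Two results are exposed. First, a small, null or reversed H2a difference could not be attributed to surface alone, and the over-ground speed offered to clinicians for prescribing exercise would be an average over a short course with turns. Second, a turning stride has an inside and an outside leg. If such strides enter the Aim 7 over-ground analysis, they add side-to-side differences unrelated to straight walking.

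**Working it through.** The plan gives no figure for turning and no sample-size calculation for H2, so there is nothing to reproduce. The check is direct arithmetic.

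**Inputs from the documents.** Course length 20 m; stage length 150 s; pilot self-selected speeds 0.88 m/s (K3) and 1.16 m/s (K4); pilot fast speeds 1.15 and 1.53 m/s; cited 3-MET speed 1.47 mph = 0.657 m/s. Pilot speeds stand in for the self-chosen corridor speeds, which are not known in advance.

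**Turns per stage** = whole part of (speed × 150 / 20), before any time lost:

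| Speed | Distance | Turns |
|---|---|---|
| 0.66 m/s (75% of 0.88) | 99 m | 4 |
| 0.88 m/s | 132 m | 6 |
| 1.15 m/s | 172.5 m | 8 |
| 1.16 m/s | 174 m | 8 |
| 1.53 m/s | 229.5 m | 11 |

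If each turn also takes 3 s, the extremes become 150/(20/0.66 + 3) = 4.5 and 150/(20/1.53 + 3) = 9.3, so 4 and 9 turns.

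**Time lost per turn (assumption; not in the documents).** Suppose a straight-line speed v costs 3 METs, and each turn loses t seconds while oxygen uptake stays at the straight-walking level. The distance/time speed at 3 METs is then 20 / (20/v + t). At v = 0.657 m/s, 20/v = 30.43 s:

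| t | Recorded speed | Shift |
|---|---|---|
| 0 s | 1.47 mph | 0% |
| 0.5 s | 1.45 mph | -1.6% |
| 1 s | 1.42 mph | -3.2% |
| 2 s | 1.38 mph | -6.2% |
| 3 s | 1.34 mph | -9.0% |
| 3.5 s | 1.32 mph | -10.3% |

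The proportion grows with speed. For t from 0.5 to 3 s it is 2.2% to 11.7% at 0.88 m/s and 2.8% to 14.8% at 1.16 m/s.

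**Extra oxygen cost (assumption).** If turning instead raises net walking cost by a fraction f with no time lost, the 3-MET speed becomes v/(1 + f). For f of 2% to 10% it is lower by 2.0% to 9.1%.

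**The zero case.** If uptake falls as the walker slows, along the same straight line (uptake = a + b × speed), then mean uptake = a + b × mean speed. The stage average still lies on the line, and distance/time speed has no bias.

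**Straight-segment speed with whole-stage uptake.** In that same zero case, the straight-segment speed matching a mean of 0.657 m/s is 20 / (30.43 - t). For t = 1 s this is 0.679 m/s (+3.4%); for t = 3 s it is 0.729 m/s (+10.9%). Pairing it with uptake averaged over the whole stage would overstate the over-ground 3-MET speed, in favour of H2a.

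These shifts are not converted to power, because the plan gives no expected H2 difference, no standard deviation for it and no named test of treadmill against over-ground.

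**The case against.** The strongest reply is that the documents establish the turns but not their effect. The seconds lost and the oxygen cost per turn are not given, and the shift may be zero. That stands, and it is why the size is shown as a range from zero. The over-ground method is also said to follow prior studies, and Section 5 already acknowledges that the two conditions differ. Neither statement says how turns are handled. Pacing differs as well (self-chosen against a fixed belt speed), so turning is not the only difference bundled with surface.

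A reader might infer more than the documents support:

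- *Over-ground speed can only be distance over time.* No formula is given, and the sensors record stride velocity, so another derivation is possible.
- *The bias also works against H2b.* Cadence is steps per minute. Distance lost at a turn does not enter it, and the effect of turning steps on the cadence at 3 METs cannot be signed.
- *Faster controls carry more turning cost in Aim 3(a).* No control speeds are given, both groups walk the same course, and cost per turn may differ between groups. No net direction follows.
- *A null H2a would be due entirely to the course.* That depends on an unknown turning cost and an unknown true difference. The expected bias would mask H2a; it would not falsely confirm it.
- *Aim 7 necessarily includes turning strides.* The walkway trials supply a second over-ground sensor data set, and the plan does not say which one is used.

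**Conclusion.** The confound in H2 is real: about 4 to 11 reversals per stage over-ground, none on the treadmill, and nothing in the procedures or the Aim 2 analysis that separates turning from surface. If over-ground speed is distance over time, the likely direction is an understated over-ground 3-MET speed, against H2a. Near 1.47 mph the time-loss calculation gives 0% to about 9-10%. The upper end assumes 3-3.5 s lost per turn with uptake unchanged; the lower end assumes slowing along the same oxygen-speed line at no added cost. H2b is confounded in an unknown direction. Aim 7 over-ground asymmetry may be contaminated, depending on which strides are analysed. The issue calls for added analysis and narrower wording; it does not invalidate the test.

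**What to change.** 1. Log the number of turns in each over-ground stage.
2. State in Section 10 that the primary Aim 2 measures are recorded distance divided by stage time and tallied cadence, so that both cover the same period as whole-stage oxygen uptake.
3. Add a sensitivity analysis using straight-segment speed and cadence from the sensors already worn. Report it beside the primary result as a bound. The two bracket the answer if uptake in turns lies between the slowed-walking and straight-walking levels. If turning adds oxygen cost beyond that, both may be low.
4. Compute Aim 7 over-ground asymmetry from straight-walking strides only, and name the source (corridor straight segments or walkway trials).
5. Word the H2 conclusion as 20-m corridor walking with turns versus treadmill walking, not as surface alone.

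The cost is a turn tally, one processing step on sensor data already planned, and a few sentences of text; no visit or equipment is added. The downsides are that turning strides are dropped from Aim 7, and that straight-segment speed set against whole-stage uptake can err in the opposite direction, so it should not replace the primary measure.

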Hypotheses: For both adults with and without a below-the-knee amputation (after controlling for covariates):

H4a: Comorbidities: Energy expenditure will be significantly greater at all walking speeds and for both walking conditions (over-ground and treadmill) for adults with greater comorbidity burden as assessed with the Cumulative Illness Rating Scale.

H4b: Fatigue: Energy expenditure will be significantly greater at all walking speeds and for both walking conditions (over-ground and treadmill) for adults who indicate fatigue on the PROMIS-29, as compared to those who do not indicate fatigue.

H4c: Sleep Disturbance: Energy expenditure will be significantly greater at all walking speeds and for both walking conditions (over-ground and treadmill) in adults who indicate sleep disturbance on the PROMIS-29, as compared to those who do not indicate sleep disturbance.

H4d: Balance: Energy expenditure will be significantly greater at 125% of self-selected gait speed for treadmill walking in individuals with balance deficits, as indicated by decreased Functional Reach Test distance and decreased time until loss of balance during the modified Clinical Test of Sensory Integration in Balance conditions 3 and 4 (foam, eyes open and foam, eyes closed).

H4e: Functional Lower Extremity Strength: Energy expenditure will be significantly greater for self-selected and 125% of self-selected walking speed for both walking conditions (over-ground and treadmill) in adults with decreased functional lower extremity strength, defined as slower 5 Times

Repeated Chair Rise times.

H4f: Functional Mobility: Energy expenditure will be significantly greater at for walking at 125% of self-selected speed for both walking conditions (over-ground and treadmill) in adults with decreased functional mobility, defined as increased L-test time.

H4g: Agility: Energy expenditure will be significantly greater for walking at 125% of self-selected speed for treadmill walking in adults with agility deficits, defined as slower Four Square Step Test times and Figure-of-8 Walk Test times.

We expect that relationship may be stronger among adults with a unilateral below-the-knee amputation, but we are not powered to explore between-group differences. In fact, Aim 4 (and Aim 5) is (are) exploratory, and we are looking for trends in differences.

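### The over-ground walking test does not impose the 75% and 125% speeds at which Aim 3/H3(a), and at 125% H4e and H4f, are stated, and the analysis plan does not link the two

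*Combined protocol and SAP*

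**What the plan says.** In the combined protocol and SAP, section 5 (Research Abstract), Specific Aim 3 sets the comparison between adults with an amputation and controls "during short bouts of over-ground and treadmill walking at self-selected gait speeds, 75% and 125% of self-selected gait speeds". H3 gives no percentages of its own and takes its speeds from the aim: "Energy expenditure will be significantly greater at all walking speeds for adults with a limb amputation as compared to controls (a) over-ground", and likewise on the treadmill.

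Within Aim 4, two hypotheses name a percentage over-ground:

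- H4e: "Energy expenditure will be significantly greater for self-selected and 125% of self-selected walking speed for both walking conditions (over-ground and treadmill").
- H4f: "walking at 125% of self-selected speed for both walking conditions (over-ground and treadmill").

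Section 6 (Procedures) describes two tests. The treadmill test sets the belt to 75%, 100% and 125% of the person's GAITRite self-selected speed, for 2.5 minutes each. The over-ground test, on a course between two cones 20 metres apart, asks for a *slow* stage, then a *usual, comfortable* stage, and finally: "In stage 3, participants will be asked to walk at their “brisk” speed for 2.5 minutes". It gives no target, pacing or tolerance. Distance covered in each stage is recorded.

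Section 10 (Data) plans MANOVA/MANCOVA with follow-up ANOVAs/ANCOVAs for Aim 3, and regression with non-modifiable covariates for Aim 4. Neither mentions achieved speed.

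**The concern.** The percentage of self-selected speed is part of the definition of the outcome in Aim 3, H4e and H4f. Oxygen use depends on walking speed; Aim 2, which looks for the speed that corresponds to 3 METs, rests on that. On the treadmill the relative speed is fixed by design. Over-ground each person chooses it in the slow and brisk stages, and it may differ between people and between groups.

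H3(a) is therefore at risk of being reported as a group difference at 75% and 125% when the data show a difference at two self-chosen efforts. That contrast combines the cost of walking with an amputation and how far each group slows down or speeds up on instruction. Treadmill and over-ground results would also carry the same 125% label for workloads that need not match. If the link between stages and percentages stays open, it will be settled after the data are seen.

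**Working it through.** **Hypotheses against procedures**

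| Statement | Over-ground speeds named | Over-ground procedure |
|---|---|---|
| Aim 3/H3(a) | 75%, 100%, 125% | *slow*, *usual, comfortable*, *brisk*; only 100% has a counterpart in substance |
| H4a–c | all walking speeds, no percentage | no conflict in wording |
| H4d, H4g | none (treadmill only) | not affected |
| H4e | 100%, 125% | 125% not imposed |
| H4f | 125% | 125% not imposed |

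H4a shows the wording without a percentage: "Energy expenditure will be significantly greater at all walking speeds and for both walking conditions (over-ground and treadmill) for adults with greater comorbidity burden". H4d shows the restriction to the treadmill: "Energy expenditure will be significantly greater at 125% of self-selected gait speed for treadmill walking in individuals with balance deficits". The mismatch is thus confined to 75% and 125% in Aim 3/H3(a) and to 125% in H4e and H4f.

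**How far might *brisk* be from 125%?** The documents give no stated figure to reproduce. The only relevant data are the pilot mean speeds in the treadmill test description (44 patients with a unilateral transtibial amputation):

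- K3: self-selected 0.88 m/s (95% CI 0.80 to 0.95), fast 1.15 m/s (1.05 to 1.25).
- K4: self-selected 1.16 m/s (1.06 to 1.25), fast 1.53 m/s (1.38 to 1.68).

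Assumption: *brisk* resembles the pilot fast speed. The documents do not say so.

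1. Ratio of fast to self-selected mean: K3 1.15/0.88 = 1.307; K4 1.53/1.16 = 1.319.
2. Speed at 125%: K3 1.25 × 0.88 = 1.10 m/s; K4 1.25 × 1.16 = 1.45 m/s.
3. Excess over 125%: K3 1.15 − 1.10 = 0.05 m/s, or 0.05/1.10 = 4.5%; K4 1.53 − 1.45 = 0.08 m/s, or 0.08/1.45 = 5.5%.
4. Crude extremes from opposite confidence limits: K3 1.05/0.95 = 1.11 to 1.25/0.80 = 1.56; K4 1.38/1.25 = 1.10 to 1.68/1.06 = 1.58. These are wide bounds on a ratio of means. They do not describe the spread between individuals.

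There is no pilot figure for a slow speed and none for controls, so neither the distance of *slow* from 75% nor a difference between groups can be computed.

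**Can achieved speed be recovered?** Yes: mean stage speed = distance/150 s. At 0.88 m/s a person covers 0.88 × 150 = 132 m, and 132/20 = 6.6 lengths, which means about six turns. Distance-based speed may therefore understate straight walkway speed. A percentage of the person's own over-ground *usual* stage avoids part of that problem, because the course and its turns are the same.

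**The case against.** The strongest reply is that *slow*, *usual* and *brisk* are a self-paced counterpart of the treadmill stages, and that Aim 3 is merely loosely worded. The over-ground test is introduced as similar to the treadmill test, and the treadmill percentages were chosen with pilot self-selected and fast speeds in view. This is a fair reading of the intent, and it supports a correction of wording over a redesign. It does not remove the contradiction, because no section equates the labels with the percentages.

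Three further objections stand and limit the point.

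- A reader might infer that the over-ground endpoints are never measured. That goes too far: oxygen use is collected in all three over-ground stages, the *usual, comfortable* stage is in substance the self-selected condition, and recorded distance allows achieved speed to be derived.
- A reader might infer that less mobile participants will speed up less and so pull the associations toward zero, or that controls' greater reserve will shrink or reverse the H3(a) contrast. The documents do not show this. The pilot ratios are nearly equal at the two functional levels (131% and 132%), and there are no control speeds.
- Exact percentages would not equalise absolute speed. Groups with different self-selected speeds walk at different absolute speeds on the treadmill as well. Only variation in relative speed is at issue.

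**Conclusion.** The inconsistency is real and narrow. The over-ground conditions at 75% and 125% in Aim 3/H3(a), and at 125% in H4e and H4f, are not implemented by the over-ground test, and the analysis section supplies no link. Two of the three over-ground conditions in Aim 3 are affected. This matters most for H3(a), since Aim 3 is not labelled exploratory while section 5 declares Aim 4 to be so.

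As for size, if *brisk* equals the pilot fast speed, the mean is about 131% to 132% of self-selected speed, roughly 5% above the 125% target. The gap for *slow*, the spread between individuals, and the size and direction of any bias between groups cannot be determined from the documents.

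A reader might extend the point to the whole of H4. The text does not support that: H4a–c name no percentage, and H4d and H4g concern the treadmill only. The treadmill half of H3 is also unaffected.

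**What to change.** Reconcile sections 5, 6 and 10 before the analysis:

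1. Restate the over-ground conditions in Aim 3/H3(a), H4e and H4f as slow, usual and brisk. Keep the percentages for the treadmill, and make no over-ground claim at 75% or 125%.
2. Add to section 10 that achieved over-ground speed per stage is distance/150 s. Report it by group, both as a percentage of the person's own over-ground *usual* stage and as a percentage of GAITRite self-selected speed. GAITRite is run before and after each condition, so name the collection that serves as reference.
3. As a prespecified sensitivity analysis, either adjust for achieved relative speed or interpolate each person's oxygen use to 75% and 125% from the three stages. Flag extrapolated values, which arise when *brisk* falls below 125% or *slow* lies above 75%.

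The cost is a wording change and a short derivation from data already planned; no visit or measurement is added. The downsides are that the over-ground claim becomes less specific, and that speed from a 20-metre course with turns may understate walkway speed. Percentages of GAITRite speed are therefore imprecise, which is why the interpolation should stay secondary.
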